## V. SIGNIFICANCE:

The proposed project has potential to yield results critical to developing rapid-acting antidepressant medications based on the ketamine model. Specifically, if our results indicate

**Figure 1. The Study Drug Effect on Montgomery Åsberg Depression Rating Scale (MADRS).** (A) There is a significant main effect of time ( $F_{(8,245)} = 43.5, p < 0.0001$ ), demonstrating significant decrease in MADRS scores from baseline. There is also significant interaction between treatment and time ( $F_{(8,245)} = 2.0, p = 0.04$ ), with overall reduction in depression scores following treatment with rapamycin+ketamine (Rapamycin; blue line), compared to post placebo+ketamine (Placebo; red line). (B) Response rate was significantly higher following treatment with rapamycin+ketamine (Rapamycin; blue), compared to post placebo+ketamine (Placebo; red). NOTES: Response was defined as 50% improvement in MADRS from baseline; Error bars are standard errors of mean (SEM);  $d'$  = Cohen's  $d'$  effect size compared to pretreatment MADRS scores; Comparison at each time point is marked with \* for  $p \leq 0.05$  and t for  $p = 0.12$ ;

synergistic antidepressant effects, then we can pursue the combination of immunosuppressant and antidepressant therapy as a new approach to the treatment of depression. If we see antagonist effects of sirolimus on ketamine, then we will have learned that stimulating the mTOR signaling pathway is critical to the antidepressant effects of ketamine, resolving a major controversy in the field and implicating drugs facilitating mTOR signaling in the treatment of depression.

This proposal has potential to provide critical insights into the mechanisms of ketamine's antidepressant effects thus advancing our understanding of the neurobiology of depression and informing novel drug development for a new generation of rapid-acting antidepressants.

## VI. RESEARCH PLAN:

This project will be divided into three phases as described below:

### Phase One: Open Label

We anticipate recruiting 3 male or female Veterans or civilians, between the ages of 21-65 years, for an open-label, extended-observation trial in order to first evaluate the safety of combining Ketamine with Sirolimus (same inclusion/exclusion criteria, recruitment procedures, and assessments as detailed below under Phase two of the study). Specifically, we will implement a 10- hour post-Sirolimus observation period that will take place in the Biostudies Unit (9th floor, building 1). Participants will then be asked to return to Biostudies on the morning following the administration of Rapamycin and Ketamine for additional assessment. Transportation will be arranged from Biostudies to the participants' homes and back to Biostudies the following day. In addition, the participants will be provided with a direct telephone number that they can use at any time between the end of the 10-hour observation phase and their appointment on the following day so they can contact a study psychiatrist in case of emergency or adverse effects. For 7 days after the treatment, a study clinician will contact subjects daily to inquire about side effects or interaction

effects that participants may be experiencing as a result of the study medications. The Phase One procedures are further detailed below:

## **Phase One Research Procedures**

### ***Day 1:***

**T-130 min:** Subjects will present to the VACHS to complete vitals and provide a urine sample for drug and pregnancy testing.

**T-120 min:** Subjects will receive a single 6 mg oral dose of sirolimus. They will be monitored for any acute allergic reaction or other adverse event. Clinical assessments administered including PSWQ, PSQI, MADRS, QIDS-SR, CGI, HAM-A, CADSS, PANSS (assessment measures are described below).

**T-60:** Intravenous lines started.

**T 0\*:** Blood draw for sirolimus level. Ketamine infusion begins (0.5 mg/kg infused over approximately 40 minutes). Subjects will be monitored closely by study physician and nurse.

**T+15:** Blood draw for sirolimus and ketamine levels.

**T+30:** CADSS, PANSS.

**T+40:** Blood draw for sirolimus and ketamine levels.

**T+60\*\*:** MADRS, QIDS-SR, CGI.

**T+120:** CADSS, PANSS, MADRS, QIDS-SR, CGI.

**T+230:** MADRS, QIDS-SR, CGI, HAM-A.

Ten hours post sirolimus administration, subjects will be evaluated by a study physician or APRN and will be medically cleared for discharge. Subjects will be provided with a study physician's direct telephone number that they can use at any time in case of emergency or adverse effects.

\*Blood pressure, heart rate, and oxygen saturation will be recorded every 10 minutes during infusion (T0-40 minutes).

### ***Ketamine Administration Notes:***

Subjects in Phase One will receive one infusion of ketamine (0.5 mg/kg infusion over approximately 40 minutes). The ketamine dose and route of administration are similar to that seen in previous investigations and has demonstrated high safety and tolerability.

A physician who is trained and has significant experience with both ketamine and infusion studies will oversee and administer the ketamine infusions. A nurse will also be present with the subject from the insertion of bilateral cannula for drug infusion and blood sampling, through to recovery following ketamine infusion.

### ***Sirolimus Administration Notes:***

Subjects will receive a single 6 mg oral dose via oral solution of sirolimus approximately two hours prior to the Ketamine infusion. The sirolimus dose will be given in 2 ounces of orange juice with 4oz of water. As for the tolerability of single dose of sirolimus, based on data in healthy subjects and consultation with [name], Director of Transplant Medicine, Yale University, an expert with sirolimus treatment, it is expected that a single 6 mg oral dose will produce minimal adverse effects.

**Day 2 /Follow-Up:**

Subjects will present to the VACHS to complete clinical assessments and a brief cognitive assessment. Procedures for this 24-hour follow-up will be identical to Phase Two follow-up procedures described below; however, subjects who participate in this 24-hour follow-up for Phase One will not receive any medications or infusions at follow-up. They will be asked about any residual side effects of other adverse events (AEs) and any appropriate referral for treatment will be made as necessary. Transportation to and from Biostudies will be arranged.

**Days 3-7/ Phone Follow-Up:**

After the Day 2 in-person follow-up, to further assess the safety of combined ketamine and sirolimus, a study clinician will contact Phase One participants by telephone, daily until Day 7. During these daily telephone follow-ups, subjects will be asked about potential side effects or interaction effects they may be experiencing related to the study medications.

After three participants undergo Phase One of this study, The PI will report findings and any issues to the Data and Safety Monitoring Committee (DSMC). The PI will not proceed to Phase Two of the study without a review and recommendation of continuation by the DSMC and subsequent full HSS review and approval of the DSMC's report.

Note: Participation in Phase One will not exclude subjects from participating in Phase Two if they so choose.

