**A. Phase Two Research Procedures (following DSMC approval) Subjects:**

We anticipate recruiting and screening approximately 75 male and female Veterans and non-Veterans/civilians, between the ages of 21-65 years, in order to meet our target enrollment goals. In order to account for subject dropouts and the potential need to discontinue subjects before study completion (see below for discontinuation criteria) and retain a sample of 30 subjects completing the double-blind treatment phase, 45 eligible subjects who meet criteria for Major Depressive Episode as determined by the Mini International Neuropsychiatric Interview (MINI) the study inclusion criteria outlines below, will be randomized into the study. Note, this study will not include a healthy control group as we are interested specifically in the antidepressant effects of ketamine and sirolimus and therefore require subjects with current depression.

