### **Research Plan and Study Procedures:**

This is a double blind, placebo-controlled, crossover, randomized controlled trial investigating the impact of sirolimus on ketamine's antidepressant effects in participants with antidepressant-resistant depressive symptoms. Participants will be treated twice with ketamine 0.5 mg/kg infused over 40 minutes, combined with a single dose of sirolimus 6 mg orally or placebo. The 2 infusions of ketamine are separated by at least 2 weeks interval because based on previous studies the majority of patients return to their baseline depression severity within this time period. A description of each study visit is provided here and summarized in Figure 3. See Table 1 for detail regarding the schedule of study events.

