***Sirolimus or Placebo Dosing:***

Subjects will receive a single 6 mg oral dose via oral solution of sirolimus or a dose of placebo approximately two hours prior to the infusions. As above, the order of placebo and sirolimus is randomized. The sirolimus dose as well as the placebo solution will be given in 2 ounces of orange juice, followed by 4 oz of water. As for the tolerability of single dose of sirolimus, based on data in healthy subjects and consultation with [name], Director of Transplant Medicine, Yale University, an expert with sirolimus treatment, it is expected that a single 6 mg oral dose will produce minimal adverse effects.

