**If you answer a call from someone interested in the Sirolimus and Ketamine study, start here:**

*"Thank you for your interest in our study. May I tell you a little about the study? We are currently enrolling eligible Veterans and civilians in a research project to study the impact of sirolimus on ketamine's antidepressant effects. Sirolimus is an FDA-approved drug commonly used in cancer treatment and following organ transplants. Ketamine is an FDA-approved anesthetic drug shown to have rapid antidepressant effects. As this study is exploring the interaction between these two medications and their impact on depressive symptoms, we will be recruiting individuals who have current depression and have tried at least one antidepressant in the past with little to no success at improving symptoms. This study is a randomized, controlled trial in which it is expected most participants will receive two ketamine infusions, one with sirolimus and one with placebo, an inactive "sugar pill." The order in which you receive these will be based on the way you are randomized into the study. The infusion days will happen here at the VA and will be separated by approximately two-weeks. There will be follow-up assessments after each infusion to assess any changes in symptoms you may experience and to address any question or concerns you may have.*

*Does this sound like something you may be interested in? If yes, continue.*

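### Phase One participants, who have knowingly taken sirolimus solution with ketamine, may enter the double-blind Phase Two crossover; up to 3 of 30 completers may have a compromised blind, and no exclusion or analysis handles them

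*Combined protocol and SAP*

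**What the plan says.** Phase One is small and unblinded: "We anticipate recruiting 3 male or female Veterans or civilians, between the ages of 21-65 years, for an open-label, extended-observation trial". Its Sirolimus Administration Notes describe the drink: "The sirolimus dose will be given in 2 ounces of orange juice with 4oz of water". About two hours later the participant receives the ketamine infusion. The Phase One section, under Days 3-7 / Phone Follow-Up, then states: "Note: Participation in Phase One will not exclude subjects from participating in Phase Two if they so choose".

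Phase Two is introduced under Research Plan and Study Procedures: "This is a double blind, placebo-controlled, crossover, randomized controlled trial". The sirolimus dose and the infusion are the same as in Phase One. Under Sirolimus or Placebo Dosing, the masking step is: "The sirolimus dose as well as the placebo solution will be given in 2 ounces of orange juice, followed by 4 oz of water". That section does not say whether the placebo matches sirolimus in taste, smell or appearance.

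The Phase Two sample is set so as to "retain a sample of 30 subjects completing the double-blind treatment phase, 45 eligible subjects" who meet the entry criteria are to be randomised.

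Three other places bear on the point:
- The Exclusion Criteria bar known sensitivity to either drug, but not earlier exposure.
- The phone pre-screen in Appendix 1 asks whether the caller has ever taken ketamine or sirolimus, but no rule uses the answer.
- The Data Analysis section adjusts for age and sex. It has no flag, stratum or sensitivity analysis for people who came from Phase One, and no check of the blind is planned.

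**The concern.** Phase Two rests on a blinded, within-patient contrast of a rating-scale outcome. Phase One participants are the only people whom this protocol itself exposes to identified sirolimus before that contrast. They have drunk the active solution knowing what it was, and have been through the combined session. In a crossover, recognising either drink identifies both periods, so any expectancy would act directly on the sirolimus-minus-placebo difference.

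This is a stated rule that admits an avoidable risk, not a missing detail. It also affects how the reported result can be read. The figure legend in the Significance section gives the treatment-by-time interaction on MADRS as p = 0.04, which is close to the threshold. The Background section attributes the findings to Phases 1 and 2 together, and does not say whether any Phase One participant was among the Phase Two subjects. A reader cannot tell whether the question arises at all, or for how many people.

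**Working it through.** **Inputs from the documents.** Phase One n = 3 (Phase One: Open Label). Phase Two: 45 randomised, 30 completers (Phase Two Research Procedures, Subjects). Design effect d' = .53, two-sided alpha .05, 80% power, 30 patients (Data Analysis).

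**Assumed input.** The shift e in one participant's own sirolimus-minus-placebo difference if the blind fails, in SDs of the paired difference. The documents give no figure, so a range of 0.25 to 1.0 is shown.

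**1. The plan's own figures.** For a two-sided paired t-test, the noncentrality is d√n = 0.53 × √30 = 2.90 with 29 df. Power is 0.801 and the minimum detectable d at 80% is 0.529, so the stated 80% reproduces. The 45 randomised correspond to a one-third loss: 30 / (1 − 1/3) = 45.

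**2. Ceiling on the number affected.** 3/30 = 10% of completers; 3/45 = 6.7% of those randomised. The first figure is reached only if all three enter Phase Two and complete it.

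**3. Effect on the mean.** Shift in the mean = k × e / 30, where k is the number of rollover participants whose blind fails. The type I error is a normal approximation for one paired contrast with unchanged variance: 1 − Φ(1.96 − δ√30) + Φ(−1.96 − δ√30), where δ is the shift in the mean.

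| e (assumed) | Mean shift, k = 3 | Share of .53 | Type I error, k = 3 | Mean shift, k = 1 | Share of .53 |
|---|---|---|---|---|---|
| 0.25 SD | 0.025 SD | 5% | 0.052 | 0.008 SD | 2% |
| 0.5 SD | 0.05 SD | 9% | 0.059 | 0.017 SD | 3% |
| 1.0 SD | 0.10 SD | 19% | 0.085 | 0.033 SD | 6% |

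If all 45 randomised were analysed, the k = 3 type I errors would be 0.051, 0.056 and 0.073.

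**4. Power without them.** With 27 pairs the noncentrality is 0.53 × √27 = 2.75 with 26 df. Power is 0.755 and the minimum detectable d rises from 0.529 to 0.560. If Phase One participants are kept out at entry and 30 others complete, power stays at 0.801.

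**The case against.** The strongest reply is that nothing shows these people could tell the drinks apart. Both are given in orange juice followed by water, which is a masking step. The protocol expects minimal adverse effects from one sirolimus dose, and both Phase Two periods include the same ketamine infusion, whose acute effects are marked. Phase One included no ketamine session without sirolimus, so it offered no contrast to learn from. This stands: a reader might infer that the rollover participants are unblinded, and the documents do not support that.

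A reader might also infer that the bias favours sirolimus, because people who felt better would be keener to return. The documents do not support this either. Returners must again score at least 18 on MADRS, non-responders also have a reason to seek more ketamine, and the stated hypothesis allows attenuation or potentiation.

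Four further points have force:
- A shift of 0.5 to 1.0 SD is about one to two times the whole design effect.
- The planned analysis ranks the data, which limits the influence of a few extreme values. The SD arithmetic ignores this.
- MADRS is clinician-administered, and rollover does not reveal treatment order to the rater.
- Every crossover participant tastes both drinks. If the placebo is not matched, that is a wider matter which removing three people would not settle.

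The phone script's lay description of the placebo as a pill conflicts with the dosing section, but it is clerical. Participants get a liquid both times, so it does not show which is active.

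None of this supplies a safeguard. The rollover is expressly allowed, matching is not documented, and neither the entry criteria nor the analysis deals with the people concerned.

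**Conclusion.** The point holds as a possibility that the plan leaves open. Up to 3 of 30 completers (3 of 45 randomised) may enter the blinded comparison with open-label experience of the active drink, and nothing in the plan excludes them, flags them or tests their influence.

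The size is unknown. The range of 0.025 to 0.10 SD, or 5% to 19% of d'=.53, assumes that all three roll over, complete, lose the blind and shift in the same direction by 0.25 to 1.0 SD. With one such person it is 2% to 6%. At the low end the effect on type I error is negligible (0.052).

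The stated power is correct and is not in question. Nor do the documents support concluding that the reported Phase Two result is wrong. They show only that a reader cannot check whether it depends on rollover participants. If none entered Phase Two, one sentence saying so closes the matter for the completed phase.

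**What to change.** **Protocol.** Replace the note at the end of the Phase One follow-up section with a statement that people treated in Phase One do not enter the Phase Two randomised sample, so that the 30 completers come from people not treated in Phase One. A weaker alternative is to specify, before any Phase Two data are seen, that they are left out of the Phase Two analysis.

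**Completed Phase Two.** Keep the randomised primary analysis as it stands. Removing randomised participants from it once results are known would be a post hoc change of the analysis set. State how many Phase One participants were included, and report the MADRS treatment-by-time result without them, labelled as a sensitivity analysis.

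**Cost.** One changed sentence, one reported count and one re-run of the model. At entry, it means recruiting up to three more people. The 15 randomisations beyond 30 are there to cover dropout and discontinuation and should not be counted as spare. In the sensitivity analysis, removing all three leaves 27 pairs and about 75.5% power instead of 80%, so a somewhat larger p-value there would not by itself show that the blind had failed.

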**A. Phase Two Research Procedures (following DSMC approval) Subjects:**

We anticipate recruiting and screening approximately 75 male and female Veterans and non-Veterans/civilians, between the ages of 21-65 years, in order to meet our target enrollment goals. In order to account for subject dropouts and the potential need to discontinue subjects before study completion (see below for discontinuation criteria) and retain a sample of 30 subjects completing the double-blind treatment phase, 45 eligible subjects who meet criteria for Major Depressive Episode as determined by the Mini International Neuropsychiatric Interview (MINI) the study inclusion criteria outlines below, will be randomized into the study. Note, this study will not include a healthy control group as we are interested specifically in the antidepressant effects of ketamine and sirolimus and therefore require subjects with current depression.

**B. Inclusion and Exclusion Criteria:**

***Inclusion Criteria:***

1. Veterans and non-Veterans between the ages of 21-65.
2. Diagnosis of Major Depressive Episode (unipolar or bipolar) as determined by the Mini International Neuropsychiatric Interview (MINI).
3. Antidepressant-resistant depressive symptoms, defined by a history of failure of one or more adequate antidepressant trials.
4. Stable doses of antidepressants (if prescribed) for a period of four weeks or longer at the time of randomization, except for MAOIs which are prohibited (see Table 1 for exclusionary medications).

5. Stable course of psychotherapy (if engaged in) for a period of four weeks or longer at the time of randomization.
6. Females will be included if they are not pregnant or breastfeeding and agree to utilize a medically accepted birth control method (to include oral, injectable, or implant birth control, condom, diaphragm with spermicide, intrauterine device, tubal ligation, abstinence, or partner with vasectomy) or if post-menopausal for at least 1 year, or surgically sterile. For those women who are taking an oral contraceptive, we will also ask that they use (or ask their partners to use) a barrier method contraceptive.
7. Able to provide written informed consent according to VA HSS guidelines.
8. Ability to read and write in English.
9. A score greater than or equal to 18 on the Montgomery Åsberg Depression Rating Scale (MADRS).

***Exclusion Criteria:***

1. Subjects with a diagnostic history of schizophrenia or schizoaffective disorder, or currently exhibiting manic or mixed episodes or psychotic features as confirmed by the Mini International Neuropsychiatric Inventory.
2. Current, ongoing serious suicidal risk as assessed by evaluating investigator or by scoring 5 or more on the item-10 of the MADRS.
3. Patients with unstable or inadequately controlled medical conditions.
4. Patient requiring prohibited medication (see Table 1).
5. Patient with history of organ transplant.
6. Meet criteria for a diagnosis of substance dependence (amphetamines, cocaine, hallucinogens, inhalants, opioids, sedatives/hypnotics/anxiolytics) within the three months prior to screening date.
7. Positive urine drug screen for cannabis, cocaine, PCP, or barbiturates.
8. Positive pregnancy test at screening at any screen given during the study.
9. Known sensitivity to sirolimus or ketamine.
10. History of sensitivity to heparin or heparin-induced thrombocytopenia.
11. Resting blood pressure lower than 85/55 or higher than 150/95, or resting heart rate lower than 45/min or higher than 100/min.

**Table 1. Concomitant Treatments that are prohibited**

Use category	Type of medication	Details
Prohibited	MAOIs	Prohibited 4-week prior to randomization.
	VNS, ECT, deep brain stimulation	VNS, ECT, or within 6 months at randomization is exclusionary.
	Memantine	Prohibited 4-week prior to randomization.
	Barbiturates	Prohibited 2-week prior to randomization.
	Cidofovir, Mifepristone, Posaconazole, Streptozocin, Ketoconazole, Voriconazole	Prohibited 2-weeks prior to randomization and throughout the study.

